11.1.3 Safety Analysis Set

Safety analysis will evaluate the number of dropouts related to adverse events for each group

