2. STUDY RATIONALE

Despite MGD's high prevalence and impact on the general population, we still lack a standardised medical treatment for moderate to severe MGD, especially for refractory cases.

Doxycycline's main therapeutical effect on MGD inhibits the synthesis or activation of proinflammatory mediators like MMP in the corneal epithelium. Furthermore, its antimicrobial and anti-chemotactic properties are important in the lid's microbiome regulation and are crucial to optimise the meibomian gland function (improvement of meibum fluidity and glandular secretion enhancement). However, long-term use of doxycycline can be risky due to the possibility of gastrointestinal effects. Different protocols in terms of duration and dosage have been reported for doxycycline in MGD treatment, but no clear superiority of a particular protocol has been reported. [4-5] This is why, in recent years, there has been significant interest in optimising treatment protocols with lower dosage doxycycline for better tolerability without losing the therapeutical effect. [3-4] This study compares the safety and efficacy of two daily oral doxycycline protocols for refractory meibomian gland dysfunction (MGD): LCD (low-dose continuous protocol) - 50 mg of doxycycline for three months and FPP (Full-dose pulsed protocol) - 100 mg of doxycycline for the first 15 days of the month for three months.

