3.2 Secondary objective

Clinical Trial Protocol CPDOXY1

Comparison between continuous and pulsed oral doxycycline treatment protocols for refractory meibomian gland dysfunction - 9 months follow-up prospective study

To evaluate which of the protocols in the study (LCD Vs FPP) has a greater effect on patient's signs (NIBUT; TBUT, Oxford scale) on a six-month follow-up

To evaluate which protocol is related to the lower rate of adverse events

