5.3 Safety endpoints

Safety assessments will consist of recording all adverse events, adverse device effects, and product deficiencies.

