10. SAFETY AND ADVERSE EVENTS

10.1 Safety evaluation

Clinical Trial Protocol CPDOXY1

Comparison between continuous and pulsed oral doxycycline treatment protocols for refractory meibomian gland dysfunction - 9 months follow-up prospective study

During the treatment period (from V1 to V2), patients can contact any member of the study medical staff with doubts or suspected adverse events. The investigators will determine if a drug-related adverse event (AEs) has occurred.

AEs will be coded according to the most current Medical Dictionary for Regulatory Activities (MedDRA) classification.

The investigator will record the nature, severity, treatment and outcome of the AE, and will determine their association with the investigational products or procedures involved in the clinical study.

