10.4 Severity Assessment

Clinical Trial Protocol CPDOXY1

Comparison between continuous and pulsed oral doxycycline treatment protocols for refractory meibomian gland dysfunction - 9 months follow-up prospective study

The intensity (severity) of an AE is assessed by the Investigator and graded as mild, moderate or severe, irrespective of the relationship to the device or the seriousness of the event.

Mild - Discomfort noticed, but no disruption to daily activity

Moderate - Discomfort sufficient to reduce or affect normal daily activity

Severe - Inability to work or perform normal daily activity

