10.9 Collection of Adverse Events (AE)

Any AE occurring prior to signing the ICF should be considered medical history or a preexisting condition will be collected on the Medical History eCRF.

All AEs will be collected from the signing of the ICF through the 3-year follow-up and entered into the AE section of the eCRF. Serious AEs will be collected from the signing of the ICF through the 36-month follow-up and recorded on the AE eCRF. SAEs will also be reported within 24 hours using the Serious Adverse Event Report Form.

At V2, the investigator will determine whether any AE has occurred after carefully interrogating the patient. The investigator will also determine and record the seriousness, severity, relationship, and outcome for all AEs.

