11.3.3 Safety analysis

Chi-square is used for drop-out rates between groups

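### The secondary objective is the adverse event rate, but the only safety analyses the protocol names count drop-outs

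*Protocol*

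**What the plan says.** Protocol section 3.2 sets this safety objective: "To evaluate which protocol is related to the lower rate of adverse events". The data collection matches it:

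- Section 5.3: "Safety assessments will consist of recording all adverse events", along with device effects and product deficiencies.
- Section 10.1, on the treatment period from V1 to V2: "The investigators will determine if a drug-related adverse event (AEs) has occurred".
- Section 10.4: every AE is "graded as mild, moderate or severe, irrespective of the relationship to the device or the seriousness of the event".
- Section 10.9: "At V2, the investigator will determine whether any AE has occurred after carefully interrogating the patient". Seriousness, severity, relationship and outcome are recorded for each event.

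The statistical section then names two safety analyses. Section 11.1.3, although headed as an analysis set, defines no population and says: "Safety analysis will evaluate the number of dropouts related to adverse events for each group". Section 11.3.3 says: "Chi-square is used for drop-out rates between groups". Neither these sections nor any other part of the protocol describes a comparison of AE incidence between the two regimens.

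**The concern.** The named analysis has a different target from the objective. A patient who has an AE and carries on with treatment counts towards the AE rate but not towards drop-outs. All such patients are invisible in the safety result as planned. Mild AEs, which section 10.4 defines as not disrupting daily activity, are the most obvious candidates.

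This matters because section 2 presents the work as part of an interest in "optimising treatment protocols with lower dosage doxycycline for better tolerability without losing the therapeutical effect", and says the study compares both safety and efficacy. If one regimen causes more AEs that patients tolerate, while the other causes fewer AEs that make patients stop, the planned analysis shows only the second effect. The trial could then report a safety ranking that is not the ranking it set out to find.

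**Working it through.** **Figures in the plan.** The protocol gives no expected AE rate and no expected AE-related drop-out rate, so there is no safety figure to reproduce. Its one sample-size figure (11.2) concerns a paired change in break-up time: ((1.960 + 0.842) x 2.3 / 1)^2 = 41.5, so 42 by the normal approximation and 44 by the exact paired t-test, against the stated 43. That agrees closely enough and has no bearing on this point.

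**Objective against analysis.**

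| Section | Quantity | Who contributes an event |
|---|---|---|
| 3.2 | Rate of AEs | Any patient with an AE |
| 5.3, 10.1, 10.4, 10.9 | All AEs, with relationship, severity and seriousness | Any patient with an AE |
| 11.1.3 | AE-related drop-outs | Only patients who stop because of an AE |
| 11.3.3 | Drop-outs, cause not specified | Any patient who leaves; under 4.1 this includes low compliance |

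The last two rows differ from the first two, and also from each other. As worded, the one named safety test can mix tolerability with non-adherence.

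**Can the two measures disagree?** For each arm, AE-related drop-out rate = AE rate x share of AE patients who stop. The arms can have different shares, so the ranking can reverse. With assumed AE rates of 40% v 20% and assumed shares of 10% v 40%, the drop-out rates are 0.40 x 0.10 = 4% and 0.20 x 0.40 = 8%.

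The same in whole patients, splitting the 65 (section 6.1) as 32 and 33 under the 1:1 assignment in 4.1. All event counts are assumed. The interval is Newcombe's: with Wilson limits (l, u) for each proportion p,

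lower = (p1 - p2) - sqrt[(p1 - l1)^2 + (u2 - p2)^2]

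upper = (p1 - p2) + sqrt[(u1 - p1)^2 + (p2 - l2)^2]

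- Any AE, 13/32 = 40.6% (Wilson 25.5 to 57.7) v 7/33 = 21.2% (10.7 to 37.8): difference +19.4 points, 95% CI -3.0 to 39.5.
- AE-related drop-out, 2/32 = 6.25% (1.7 to 20.1) v 4/33 = 12.1% (4.8 to 27.3): difference -5.9 points, 95% CI -21.7 to 9.8.

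The point estimates rank the arms in opposite order. Both intervals include zero.

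**How precise would the AE comparison be?** Same method, near-equal assumed rates:

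| Counts | Approximate rate | 95% CI (points) | Half-width |
|---|---|---|---|
| 3/32 v 3/33 | 10% | -15.4 to 16.3 | 15.9 |
| 10/32 v 10/33 | 30% | -20.7 to 22.6 | 21.6 |
| 16/32 v 16/33 | 50% | -21.6 to 24.4 | 23.0 |

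**The case against.** The strongest reply is that AE tables, risk differences and breakdowns by relationship or seriousness usually belong in a SAP, which may exist unseen. Section 11.1.3 does not say that drop-outs are the only thing to be analysed, and all the AE data will be there. This narrows the point but does not remove it. The protocol is not silent: it names its safety analysis in two places, and neither is the quantity in 3.2. A SAP that simply carried those sections forward would leave the objective unanswered.

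Discontinuation for AEs is also a legitimate measure of tolerability, which is the word section 2 uses. That is true, and it is why the measure should be kept. It is still not the AE rate.

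The numerical example is constructed, and neither difference in it is statistically clear (Fisher p about 0.11 and 0.67). That stands. It shows only that the measures can diverge, not that they will, and it does not show that drop-out is always the less sensitive one.

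Section 4.1 says that patients who interrupt for AEs leave the study and are dropped from the analysis, without saying which analysis. The context suggests efficacy, since otherwise 11.1.3 would have nothing to count. This is a matter of clarity and secondary to the main point.

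Finally, section 10.9 refers to AE collection for 36 months, whereas visits end at day 180. The V1 to V2 window used in the fix follows the treatment period in 10.1 and the questioning at V2. The 36-month text needs reconciling separately. Likewise, the drug is taken at home, so a first dose may be hard to confirm in a patient lost before V2.

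**Conclusion.** The concern holds. The protocol fixes a safety analysis of a different quantity from the one in its own secondary objective, and its two safety statements do not agree on which drop-outs are meant. The finding comes from reading the sections together and depends on no assumed rate. The assumed counts serve only to show that the ranking can reverse (+19 against -6 points) and how wide the AE interval would be (about plus or minus 16 to 23 points). The primary endpoint is unaffected. The protocol should be corrected, because a stated objective has no matching analysis and the correction is cheap.

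**What to change.** - **11.3.3:** compare between regimens the proportion of patients with at least one AE from V1 to V2 (overall, drug-related and serious), as a risk difference with 95% CI. The choice of test can be left to the SAP.
- **11.1.3:** define the safety set as all patients who took at least one dose. Keep AE-related drop-out as a separate supportive measure.
- **Drop-out wording:** state that the test in 11.3.3 refers to AE-related drop-out, or report all-cause drop-out separately.
- **4.1:** state that the exclusion of patients who interrupt treatment does not apply to the safety analysis.
- **Interpretation:** say that the AE comparison is to be read with caution. Investigators assign the regimen without randomization, so an unadjusted difference may reflect which patients received which regimen, and about 32 patients per arm give a wide interval.

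If the sponsor really intends discontinuation as its safety measure, rewording objective 3.2 to AE-related discontinuation would also remove the contradiction, but the question about the AE rate would then be given up.

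**Cost:** wording in three sections and a little more analysis. Patients seen at V2 need no new data. Patients lost before V2 have AE information only up to their last contact, so their number per arm should be reported. The estimate may be inconclusive and is open to confounding.

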11.2 Sample size

The sample size estimate was based on a test for before-after studies using a paired t-test, defining a 1-sec change in Break-Up Time as clinically relevant and a standard deviation of 2.3 sec. Setting the error to 2.5% (one-tailed), 43 patients would be required, assuming a power of 80%. Assuming drop out, the final enrollment will be 65 patients.

Clinical Trial Protocol CPDOXY1

Comparison between continuous and pulsed oral doxycycline treatment protocols for refractory meibomian gland dysfunction - 9 months follow-up prospective study

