3. STUDY OBJECTIVES

3.1 Primary objective

To evaluate which of the protocols in the study (LCD Vs FPP) has the greatest impact on refractory MGD patient's symptoms (OSDI) on a six-month follow-up

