4. STUDY DESIGN

4.1 Study Description

This spontaneous, prospective, non-randomized, parallel-group, phase IV study was conducted in compliance with the tenets of the Declaration of Helsinki.

All study participants were fully consented, and written informed consent was obtained.

This study included patients with refractory MGD. Refractory MGD is defined as symptomatic MGD (OSDI > 13 points) despite 2 months of first-line treatment with lacrimal substitutes 3 times per day and meibomian gland expression with warm compresses twice per day.

The study will consist of 3 visits: Visit 1(Baseline - day 0), Visit 2 (day 90 ± 5 - 3rd month), Visit 3 (day 180 ± 5 - 6 month). At each visit, patients will receive an OSDI questionnaire, NIBUT, type I Schirmer test and AS assessment, including TBUT, corneal staining (Oxford scale)

At baseline, eligible patients will be enrolled and treated with the assigned protocol. The investigators will assign the protocol (non-randomized) in a 1:1 ratio.

At Visit 2, NIBUT, TBUT, Oxford scale and OSDI improvement will be evaluated compared with Visit 1. Patients will be carefully asked about their compliance with the treatment. Patients who interrupted the treatment for adverse events or low compliance (<75% of the protocol adherence) will exit the study and be excluded from the analysis.

At Visit 3, the study population will be evaluated as done in Visit 2

The protocols in the study are the following:

- LCD (low-dose continuous protocol) - 50 mg of doxycycline for three months
- FPP (Full-dose pulsed protocol) - 100 mg of doxycycline for the first 15 days of the month for three months.

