5. STUDY ENDPOINTS

5.1 Primary endpoints

The primary endpoint of this study are:

- OSDI
- Number of patients with OSDI improvement > 7 points (clinically significant)

Clinical Trial Protocol CPDOXY1

Comparison between continuous and pulsed oral doxycycline treatment protocols for refractory meibomian gland dysfunction - 9 months follow-up prospective study

For these parameters, the changes occurring in the two groups at each visit vs baseline will be evaluated.

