11.3.1.1 Primary efficacy endpoint

Paired t-test will be used to study OSDI. Chi-square is used to study clinically significant OSDI variation

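### The sample size and its 80% power rest on a before-after test of Break-Up Time, so power for the primary LCD-versus-FPP comparison on OSDI is not established

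*Protocol*

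**What the plan says.** The primary objective (section 3.1) is to find "which of the protocols in the study (LCD Vs FPP) has the greatest impact on refractory MGD" symptoms, measured by OSDI at six months. Section 4.1 describes two parallel groups: "The investigators will assign the protocol (non-randomized) in a 1:1 ratio". Section 5.1 names two primary endpoints, the OSDI score and "Number of patients with OSDI improvement > 7 points (clinically significant"), each examined as change from baseline in the two groups. Section 5.2 lists NIBUT and TBUT as secondary.

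Section 11.2 sizes the study: "The sample size estimate was based on a test for before-after studies using a paired t-test", for a 1-second change in Break-Up Time with an SD of 2.3 seconds and one-sided 2.5% error. It concludes that "43 patients would be required, assuming a power of 80"%, and then: "Assuming drop out, the final enrollment will be 65 patients". It gives no number per arm and no drop-out rate.

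For the analysis, section 11.3.1.1 says "Paired t-test will be used to study OSDI" and "Chi-square is used to study clinically significant OSDI variation".

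**The concern.** Section 11.2 is the only justification for the number of patients. It departs from the primary objective twice: in the endpoint (Break-Up Time, secondary whether TBUT or NIBUT is meant) and in the contrast (change from baseline, not LCD against FPP). The planned analysis does not close the gap for the OSDI score, because a paired t-test shows whether patients changed and not whether one regimen did better than the other.

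A reader will naturally take the 80% as the power of the comparison. If LCD and FPP then show no significant difference, the result could be read as evidence that they perform alike. The rationale in section 2, which looks for lower dosage with the benefit retained, makes that reading likely. The protocol does not let anyone judge whether 65 patients support it.

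**Working it through.** **Inputs from the protocol.** Change 1 s, SD 2.3 s (read as the SD of the within-patient change), one-sided 2.5%, 80% power, 43 required, 65 enrolled (section 11.2); two arms at 1:1 (section 4.1). The split is taken as 32/33 for 65 patients and 21/22 for 43.

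**1. Reproduce the 43.** Normal approximation: n = [SD × (z₀.₉₇₅ + z₀.₈₀) / change]² = [2.3 × (1.960 + 0.842) / 1]² = 41.5, so 42. The exact noncentral t gives power 79.5% at 43 and 80.5% at 44. The stated 43 is therefore right, to within a patient, for a single-group paired test.

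**2. Which patients the 80% covers.** If 43 were per arm, 2 × 43 = 86 would be needed, and only 65 are enrolled. The 80% can therefore be delivered only for all patients taken together. This is inferred, since section 11.2 does not say so. The implied drop-out is 1 − 43/65 = 34%. Power of the same paired test:

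| Patients | Both arms together | Within one arm |
|---|---|---|
| 43 (21/22) | 79.5% | 47% / 49% |
| 65 (32/33) | 93% | 66% / 68% |

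**3. Same Break-Up Time inputs, between arms.** With a two-sample t-test, the noncentrality is 1 / [2.3 × √(1/n₁ + 1/n₂)]. Power is 28% at 21/22 and 41% at 32/33. Changing only the contrast, with no outside figure, already removes the 80%.

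**4. Detectable OSDI difference between arms.** Two-sample t-test on change, two-sided 5%, 80% power. √(1/32 + 1/33) = 0.248 and √(1/21 + 1/22) = 0.305. Multiplying by 1.960 + 0.842 gives 0.70 and 0.85 SD by normal approximation. The exact t values are **0.706 SD (65)** and **0.875 SD (43)**. The expected 95% CI half-widths are 0.50 SD and 0.62 SD.

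The protocol gives no SD of OSDI change. Over an assumed 10 to 20 points:
- 65 patients: 0.706 × 10 to 0.706 × 20 = 7.1 to 14.1 points
- 43 patients: 0.875 × 10 to 0.875 × 20 = 8.8 to 17.5 points

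**5. Power for a 7-point difference between arms.** This is for scale only, because the 7 points in section 5.1 is a within-patient threshold.

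| Assumed SD of change | 65 patients | 43 patients |
|---|---|---|
| 10 | 79% | 61% |
| 15 | 46% | 32% |
| 20 | 28% | 20% |

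**6. Responders (improvement above 7 points).** Chi-square without continuity correction, two-sided 5%, 80% power; the lower rate is assumed.

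| Lower rate | Higher rate needed, 65 | Difference | Higher rate needed, 43 | Difference |
|---|---|---|---|---|
| 30% | 64.1% | 34.1 points | 71.6% | 41.6 points |
| 40% | 73.8% | 33.8 points | 80.6% | 40.6 points |
| 50% | 82.3% | 32.3 points | 88.3% | 38.3 points |
| 60% | 89.6% | 29.6 points | 94.7% | 34.7 points |

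**The case against.** The strongest reply is that the plan is consistent with itself: sections 5.1, 11.2, 11.3.1.1 and 11.3.1.2 all work with change from baseline, and the sizing test is the same kind of test as the primary analysis. That is true, but they agree on a test that cannot answer the objective in section 3.1. It widens the problem.

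A second reply is that the responder chi-square does compare the arms. This is the natural reading, since section 11.3.3 uses a chi-square expressly between groups and a paired t-test has no such role. If so, one primary endpoint has a between-arm test. Section 11.3.1.1 does not say so, however, and no responder rate in section 11.2 supports its power.

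Third, low power is not demonstrated. This stands. With 65 patients, 80% power for 7 points is reached at an SD of about 7/0.706 = 9.9, and the SDs and responder rates used here are assumptions. The supportable conclusion is that power is not established, not that the study is too small.

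Fourth, the 0.71 and 0.88 SD figures belong to an unadjusted two-sample test. This also stands. Adjusting for baseline would lower them: with equal variances and an assumed baseline-to-follow-up correlation of 0.5, 0.706 × √(1 − 0.5²) = 0.61 SD. The unadjusted figures are then conservative.

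Finally, assignment is not randomised, so precision is not the only limit on the comparison. That is so, but it does not make the stated 80% relevant to it.

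**Conclusion.** The concern holds. The arithmetic behind 43 is correct, but the 80% belongs to a before-after change in a secondary endpoint, and the enrolment can deliver it only over both arms together. Nothing in the protocol gives the power of LCD versus FPP on OSDI, and the paired t-test named for the OSDI score does not make that comparison.

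With an unadjusted two-sample test, the design detects 0.71 SD of OSDI change if all 65 patients contribute and 0.88 SD if 43 do. Responder differences must be about 30–34 or 35–42 percentage points. The SD-unit figures rest only on the patient numbers, the 1:1 split, 80% power and two-sided 5%. The conversions to points and the responder figures rest on an assumed SD of 10–20 and an assumed lower rate of 30–60%. The pooled reading of the 43 is an inference.

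**What to change.** 1. In section 11.2, state that the 80% refers only to the before-after change in Break-Up Time over all patients and is not the power of the primary comparison. The sponsor should confirm that reading of the 43.
2. In section 11.2, state what the enrolment can detect between arms at 80% power and two-sided 5%: 0.71 SD of OSDI change if all 65 contribute and 0.88 SD if 43 do, converted to points with a sourced SD of OSDI change. For responders, give about 30–34 (65) or 35–42 (43) percentage points for lower rates of 30–60%. If a baseline-adjusted test is chosen, label the SD figures as conservative or recompute them for that test.
3. In section 11.3.1.1, name a between-arm test of OSDI change (two-sample, or adjusted for baseline OSDI), say that the responder chi-square compares LCD with FPP, and report the LCD-minus-FPP difference with its 95% confidence interval.

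Item 2 should not go in without item 3, or section 11.2 would describe a test that is not planned. Both 43 (the protocol's own required number) and 65 are shown because sections 4.1 and 11.1.2 disagree on whether patients who leave the study are analysed. Those sections should be reconciled separately.

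The cost is wording in two sections, with no added patients, visits or data. The drawback is a less favourable statement of what the study can show.
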